## **Methodology**

Prospective, Non-randomized, Interventional, Controlled

*The Biomedical Research Ethics Committee of Peking University First Hospital* is overseeing the research. ([contact]; Email: [[contact]](mailto:[contact]); Address: [name])

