- 4) Urethral catheterization will be routinely done preoperatively
- 5) If the patient refuses to accept the novel approach before surgery, they will be directly enrolled in the traditional group. If both approaches are acceptable to the patient, the decision whether to use the novel approach will be made according to the intraoperative

conditions (see operating procedures below).

- Operating procedures

General anesthesia; Modified lithotomy position (Fig. 1a); Establishment of pneumoperitoneum: Place a trocar 1cm above the umbilicus through which to establish pneumoperitoneum and keep the abdominal pressure as 12 mmHg (millimeters of mercury).

Trocar placement: above the umbilicus (trocar C, 10 mm), upper right and left quadrants (trocars B and D, 5 mm), lower right quadrant (trocar A, 12 mm), lower left quadrant (trocar E, 5 mm), the midpoint between the pubic symphysis and umbilicus (trocar F, 5 mm).

[figure not shown]

Fig.1 Patient position and trocar placement

Abdominal exploration: Explore the abdominal cavity in accordance with the principle of non-contact, from far to near step by step, explore the tumor finally.

The mesosigmoid and mesorectum are dissected from the right lateral rectum towards the root of the inferior mesenteric artery (IMA). The IMA is transected and ligated, so is the inferior mesenteric vein. Posterior space of the descending colon is dissected following opening the peritoneum beside the left rectum. The rectum in the pelvis is mobilized from posterior rectal space, anterior rectal space to bilateral rectal space successively. The lower edge of the tumor is marked by a clamp. The linear stapler is placed in the pelvis to clamp the distal rectum below the tumor to see if the transection can be done more than 1cm from the lower edge of the tumor. If yes, the distal rectum will be transected by the traditional approach (that means the patient will be assigned to the traditional group). The proximal bowel is transected through a small midline incision. Then the coloanal

anastomosis will be done intracorporeally. A surgical drain is placed in the pelvis and a terminal ileostomy is routinely performed. All incisions are closed.

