If the distal rectal transection cannot be done more than 1cm from the lower edge of the tumor, the anterior obturator nerve gateway approach will be used (that means the patient will be assigned to the experimental group). The steps are as follows: The peritoneum covering the ureter and external iliac artery is opened more than 2 cm across the vas deferens (male) or round ligament (female). The Retzius space and vesicohypogastric fascia are exposed. The obturator vessels and obturator nerve are properly identified. Care should be taken to avoid any injury when using energy devices near the obturator nerve. The gateway is then opened through the TME (total mesorectal excision) compartment and the lateral compartment. If necessary, an “endoloop” can be placed through the gateway, and the bundled S2-4 nerves, ureter and bladder vessels are gently retracted toward the cranial direction to widen the gap. The linear stapler is placed in the gateway to vertically transect the distal rectum. The following procedures are the same with the traditional group as described above.

During the operation, the following variables will be recorded: the angle between the linear stapler and the rectum, distance from the lower edge to the resecting margin, whether the operation converted to transanal approach, operative time, bleeding volume, anastomotic height from anal verge and the length of the stapling line.

➤ **Postoperative management:**

The following information will be recorded:

1) Vital signs (body temperature, pulse rate, respiration rate, blood pressure) are routinely monitored, gross volume of fluid input and output will be recorded every 24h, blood routine, the comprehensive metabolic panel and coagulation function tests will be performed every 3 days.

2) The time of catheter removal (days after operation), residual urine volume in the bladder will be measured by ultrasound examination. Whether there is a request to be re-catheterized or take oral medication to relieve the dysuria. All patients will be asked to fulfil the IPSS (International prostate symptom score) questionnaire to assess urinary function.

**Table 1.** International prostate symptom score assessing urinary function

In the past month:	Not at All	Less than 1 in 5	Less than Half the	About Half the	More than Half	Almost Always
--------------------	------------	------------------	--------------------	----------------	----------------	---------------

		Times	Time	Time	the Time	

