1. Incomplete Emptying How often have you had the sensation of not emptying your bladder?	0	1	2	3	4	5
2. Frequency How often have you had to urinate less than every two hours?	0	1	2	3	4	5
3. Intermittency How often have you found you stopped and started again several times when you urinated?	0	1	2	3	4	5
4. Urgency How often have you found it difficult to postpone urination?	0	1	2	3	4	5
5. Weak Stream How often have you had a weak urinary stream?	0	1	2	3	4	5
6. Straining How often have you had to strain to start urination?	0	1	2	3	4	5
	None	1 Time	2 Times	3 Times	4 Times	5 Times
7. Nocturia How many times did you typically get up at night to urinate?	0	1	2	3	4	5
Total Score						

Score: 1-7: Mild 8-19: Moderate 20-35: Severe

- 3) The time of pelvic drain removal (days after operation)
- 4) Whether complicated with anastomotic leakage, ileus and long-lasting (more than 5 days) pulmonary or abdominal infection
- 5) All information of the pathologic report.
- 6) Postoperative hospital stay (days)

➤ **Postoperative chemoradiotherapy**

Radiotherapy program is the same with the neoadjuvant therapy. Chemotherapy will be advised for patients with stage II cancer accompanied with the following high-risk factors: histologically poorly differentiated with normal mismatched repair or stable microsatellite (MSS), pT4 (pathological stage T 4), vascular/nerve invasion, preoperative intestinal obstruction or perforation, ≤ 12 lymph nodes retrieved and R1 resection. The chemotherapy program is the same with neoadjuvant chemotherapy. If mismatch repair defect (dMMR) or high-level microsatellite instability (MSI-H) is confirmed by pathology, chemotherapy

will not be advised. Patients with stage III cancer will routinely receive chemotherapy.

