### **Primary outcomes**

[figure not shown]
- The degree of Angle denotes the degree of angle between the linear stapler and the longitudinal axis of the rectum when transecting the distal rectum.
- The degree of  $\Delta$ Angle represents the degree of angle between the simulated stapling line with the total mesorectal excision approach and the real stapling line with the transanterior obturator nerve gateway approach (this outcome is measured only in patients of the experimental group).
- Length of distal resection margin indicates the shortest distance between the distal border of the tumor and the edge of the distal resection.
- Rate of conversion to transanal transection and anastomosis of the rectum: For each case, whether there is a conversion to transanal transection and anastomosis of the rectum during the operation will be recorded. The gross conversion rate (No. of cases undergoing conversion/total No. of cases enrolled \*100%) for each group will be calculated immediately after the last patient's surgery.
- Rate of anastomotic leakage: Whether the patient complicates with anastomotic leakage postoperatively will be followed up till 6 months after surgery. The gross anastomotic leakage rate (No. of cases diagnosed with anastomotic leakage/total No. of cases enrolled \*100%) for each group will be calculated 6 months after the last patient's surgery. Anastomotic leakage will be diagnosed if the patient has clinically apparent leakage signs (such as the emission of gas, pus, or feces from the pelvic drain, or peritonitis) or extravasation of endoluminally administered watersoluble contrast medium according to CT.

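### The source of the distal resection margin, a primary outcome, is not named, and the only measurement described is taken in theatre with the approach known

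*Combined protocol and SAP*

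**What the plan says.** The Primary outcomes section defines the margin geometrically: "Length of distal resection margin indicates the shortest distance between the distal border of the tumor and the edge of the distal resection". It gives no measurer, time point, specimen state or data record.

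The Treatment section mentions a margin measurement once. At the end of the operating procedures it says "During the operation, the following variables will be recorded", and the list includes "distance from the lower edge to the resecting margin".

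The approach is chosen in the same operation. The stapler is placed below the tumour to see "if the transection can be done more than 1cm from the lower edge of the tumor". The text continues: "If yes, the distal rectum will be transected by the traditional approach (that means the patient will be assigned to the traditional group". The other branch, "If the distal rectal transection cannot be done more than 1cm from the lower edge of the tumor", leads to the experimental group. A patient who refuses the new approach beforehand goes straight to the traditional group.

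Under Postoperative management, the data to be collected include "All information of the pathologic report". The contents are not itemised, and the report is not linked to the primary outcome.

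Methodology describes the study as "Prospective, Non-randomized, Interventional, Controlled". No section mentions masking or an independent assessor.

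**The concern.** A length of a few millimetres to a few centimetres depends on where the tumour edge is placed, whether the tissue is stretched, and when it is measured. If it is recorded in theatre, whoever records it can know the approach. The Background section states the aim of confirming the advantages of the new approach, so a small, consistent difference in reading between the groups is a realistic risk.

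The Statistics section plans only unadjusted two-group tests for quantitative data. Such a test cannot tell a true difference in margin from a difference in how margins were read. A source less exposed to this may already be in the data, since the pathology report is collected, but nothing directs the analysis to it.

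**Working it through.** **Setting the sections side by side**

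| Question | Primary outcomes | Treatment, operating procedures | Treatment, postoperative management |
|---|---|---|---|
| Is a margin length named? | Yes, defined | Yes, in the list of recorded variables | Not named; full pathology report collected |
| When is it taken? | Not stated | During the operation | After surgery, if reported |
| Who takes it? | Not stated | Not stated; theatre staff, by timing | Not stated; a pathologist, if reported |
| Is the approach known to the reader? | Not stated | Can be, as it was just chosen | Not stated |
| Is it the value analysed? | Not stated | Not stated | Not stated |

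Two facts follow. The source of the primary value is undefined, and the only measurement described is unmasked.

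**Size, as an illustration only**

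The plan has no figure to reproduce here. The Sample size section gives 100 experimental and at least 100 control patients, without alpha, power, effect or SD.

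Inputs:
- n = 100 per group, from Sample size (controls taken at their minimum).
- Two-sided alpha of 0.05, assumed.
- SD of the margin of 5, 8 or 10 mm, assumed.
- b, a systematic difference in reading between the groups, of 1 or 2 mm, assumed.
- No true difference.

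Formulas (normal approximation):
- SE = SD × √(2/100)
- False-positive rate = Φ(b/SE − 1.96) + Φ(−b/SE − 1.96)

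For SD 8 mm and b = 2 mm:
- SE = 8 × 0.1414 = 1.13 mm
- b/SE = 2/1.13 = 1.77
- Rate = Φ(−0.19) + Φ(−3.73) ≈ 0.42

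| Assumed SD | SE | b = 1 mm | b = 2 mm |
|---|---|---|---|
| 5 mm | 0.71 mm | 29% | 81% |
| 8 mm | 1.13 mm | 14% | 42% |
| 10 mm | 1.41 mm | 11% | 29% |

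Without bias the rate would be 5%. At SD 8 mm the smallest significant difference is 1.96 × 1.13 = 2.2 mm. A reading shift of 2.3 mm does not guarantee significance: 2.3/1.13 = 2.03, and Φ(2.03 − 1.96) ≈ 0.53, so the test would be significant about half the time.

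**The case against.** The strongest reply is that the plan never says the theatre value is the one analysed. The definition fits a specimen measurement equally well, and a ruler laid on the fresh specimen in theatre would also count as recorded during the operation. This stands. A reader might infer that the primary outcome is a subjective length taken by the originator of the technique. The documents do not support that: no method or recorder is given, and the study is multi-center.

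A reader might also infer that a pathology measurement of the margin already exists for every patient. That is not supported either, because the plan does not name a margin length among the contents of the report. The length has to be requested, and for patients already operated on it has to be looked for.

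A third reply is that pathology cures less than it seems to. The stapler test and the outcome concern closely related distances, though not the same one: the test asks what is feasible through the usual route, and the outcome is the margin finally achieved. Allocation by that test confounds the comparison whoever reads the margin. This stands in full, and the issue needs its own remedy.

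The pathology source also has faults of its own. A fixed specimen may read shorter, and not necessarily equally in both groups, since the groups are not randomized and neoadjuvant treatment varies. Masking may be partial: the plan contrasts oblique with vertical transection, so the cut edge itself may show the approach.

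None of these replies defends leaving the source of a primary outcome unstated.

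**Conclusion.** The point holds as a modest, inexpensive improvement. The plan does not name the source of a primary outcome, and the only measurement it describes is recorded when the approach is known, so that value is open to observer bias. That theatre staff do the recording is inferred from the timing, not stated.

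The direction and size of any bias cannot be derived from the documents. The false-positive rates above, 11% to 81% across the assumed values, show only that a differential reading of 1 to 2 mm could matter at this sample size. They are not estimates for this trial, because neither the SD nor the bias is given.

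The conclusion concerns observer bias alone. It does not show that the margin comparison would be valid with a pathology reading, since the confounding from the stapler test remains.

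**What to change.** In Primary outcomes, name the specimen measurement in the pathology report as the source for the margin comparison. On the pathology request form:
- ask for this length;
- ask for the specimen state, fresh or fixed;
- leave the approach off.

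Keep the theatre value as supportive. Report the agreement between the two by group, for example as the mean difference with 95% limits of agreement. If the mean difference is not the same in the two groups, that signals differential reading or differential shrinkage, although it cannot separate the two.

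For patients already operated on (the study start is given as 2020-12-01, before the protocol date of 2021/9/7), use the existing report where it gives the length, and state how many reports do not.

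The cost is a change of wording in the plan and in the request form. No extra assessor, procedure or patients are needed. The downsides are shorter readings on fixed specimens, possibly unequal between groups; imperfect masking; missing lengths in reports already issued; and the effort of having every centre report the length in the same way.

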## Objective

To confirm the safety, feasibility and advantages by comparing the perioperative variables, postoperative functional and oncological outcomes of patients with ultralow rectal cancer treated by laparoscopic traditional distal rectal dissection vs. by transanterior obturator nerve gateway approach.

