## Follow-up

1) Information on general medical history and physical examination will be collected every 3 months for 3 years

2) Blood tumor markers of CEA (carcinoembryonic antigen) and CA19-9 (carbohydrate antigen 19-9) will be tested every 3 months for 3 years

3) Abdominal and pelvic ultrasound and chest X-ray examinations will be carried out every 3 months for 3 years

4) Abdominal and pelvic MRI or contrast enhanced CT scan will be done every year for 3 years

5) Colonoscopy will be performed within 1 year after surgery. If there is any abnormality, reexamination will be required within half a year. If no abnormality is found, once a year for 3 years. All new-found adenomas by the colonoscopy during follow-up are recommended to be resected.

6) Sexual function score is assessed by filling in the questionnaire (IIEF-5) both preoperatively and 1 year later since operation.

**Table 2.** International Index of Erectile Function-5 assessing sexual function

Over the past 6 months:					
1. How do you rate your confidence that you could get and keep an erection?	Very low 1	Low 2	Moderate 3	High 4	Very high 5
2. When you had erections with sexual stimulation, how often were your erections hard enough for penetration?	Almost never/never 1	A few times (much less than half the time) 2	Sometimes (about half the time) 3	Most times (much more than half the time) 4	Almost always/always 5
3. During sexual intercourse, how often were you able to maintain your erection after you had penetrated (entered) your partner?	Almost never/never 1	A few times (much less than half the time) 2	Sometimes (about half the time) 3	Most times (much more than half the time) 4	Almost always/always 5
4. During sexual intercourse, how difficult was it to maintain your erection to completion of intercourse?	Extremely difficult 1	Very difficult 2	Difficult 3	Slightly difficult 4	Not difficult 5

5. When you attempted sexual intercourse, how often was it satisfactory for you?	Almost never/never 1	A few times (much less than half the time) 2	Sometimes (about half the time) 3	Most times (much more than half the time) 4	Almost always/always 5
IIEF-5 scoring:					

The IIEF-5 score is the sum of the ordinal responses to the 5 items.

22-25: No erectile dysfunction

17-21: Mild erectile dysfunction

12-16: Mild to moderate erectile dysfunction

8-11: Moderate erectile dysfunction

5-7: Severe erectile dysfunction

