7) 3-year tumor-free survival (month): The time from operation to confirmation of tumor's local recurrence or distant metastasis. The end point of the patient lost to follow-up is the date of loss. 30 days is defined as one month

8) 3-year overall survival (month): The time from operation to death. The end point of the patient lost to follow-up is the date of loss. 30 days is defined as one month

9) Stoma closure time (months since operation). Anal function is assessed by Wexner scale 3 months and 12 months after stoma closure, respectively.

**Table 3.** Wexner score assessing anal function

Type of Incontinence	Frequency				
	Never	Rarely	Sometimes	Usually	Always
Solid	0	1	2	3	4
Liquid	0	1	2	3	4
Gas	0	1	2	3	4
Wear Pad	0	1	2	3	4
Lifestyle altered	0	1	2	3	4

Never - 0

Rarely - Less than once a month

Sometimes - Less than once a week or once a month

Usually - Once a day or once a week

Always - Once a day or more

Score: 0 Perfect; 20 Complete Incontinence

(As to possible risks and benefits of participating in this trial, see details in the *informed consent document*.)

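### Infection is recorded as a complication only if it lasts more than 5 days, with no severity grade and no stated observation window, so short but severe non-leak infections are missing from the safety comparison

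*Combined protocol and SAP*

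**What the plan says.** The Objective is "To confirm the safety, feasibility and advantages by comparing the perioperative variables, postoperative functional and oncological outcomes" between the two approaches. Under Treatment, the postoperative management list opens with "The following information will be recorded", and its item 4 is "Whether complicated with anastomotic leakage, ileus and long-lasting (more than 5 days) pulmonary or abdominal infection". The same list holds vital signs, catheter and drain removal, the urinary symptom questionnaire, the pathology report and length of stay. It has no closing date.

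Leakage is handled more fully under Primary outcomes: "Whether the patient complicates with anastomotic leakage postoperatively will be followed up till 6 months after surgery". It can be diagnosed from gas, pus or feces coming through the drain, from peritonitis, or from contrast extravasation on CT, with no minimum duration.

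Follow-up gives "3-year overall survival (month): The time from operation to death" and, as its first item, "Information on general medical history and physical examination will be collected every 3 months for 3 years". Complications are not named in that item. The text available contains no severity grading, no general adverse-event section, no readmission or reoperation item and no perioperative mortality outcome.

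**The concern.** A safety comparison should count the events that harm patients most. Item 4 sorts infections by how long they last, which is a poor stand-in for severity: a serious infection may be controlled quickly or be fatal quickly, and a trivial one may linger.

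Item 4 is the only named list of general complications, so what it omits has no other designated place. The experimental approach adds dissection (the Retzius space and a gateway between the mesorectal and lateral compartments), so an infected collection without a leak is a plausible harm of the new technique. If it were drained and settled in 4 days, it would not meet item 4. It would not be leakage either, unless it showed the leakage signs or contrast extravasation.

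The item also leaves open how the 5 days are measured (fever, treatment or laboratory results) and until when infection and ileus are looked for. In a multi-center study, sites may settle both questions differently.

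**Working it through.** **What the rule captures.** No figure in the plan can be reproduced on this point: the sample size of 100 and at least 100 is given without event rates, alpha or power. The check is therefore to take each type of event through the outcomes that could record it.

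| Event | Item 4 infection | Leakage (to 6 months) | Overall survival |
|---|---|---|---|
| Mild chest infection, 6 days | counted | no | no |
| Severe chest infection, resolved by day 4 | not counted | no | no |
| Pelvic collection without leak signs, settled in 4 days | not counted | no | no |
| Abdominal infection with peritonitis or pus from the drain, any duration | only if over 5 days | counted | no, unless fatal |
| Non-leak infection fatal on day 3 | not counted | no | death counted, cause not attributed |

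Rows 2 and 3 are lost altogether from the named outcomes. Row 5 is lost as an infection but kept as a death. Row 4 is not lost.

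**Size.** If the true infection rate is r and the rule captures a fraction f, the recorded rate is r × f and the number missed per 100 patients is 100 × r × (1 − f). The documents give neither r nor f, so everything below is assumed and shows direction only.

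With n = 100 per group, two-sided alpha 0.05 and the same f in both groups, approximate power = Φ{[|p₁ − p₂|√n − 1.96√(2p̄(1 − p̄))] / √[p₁(1 − p₁) + p₂(1 − p₂)]}, where p₁ and p₂ are the recorded rates and p̄ is their mean.

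| f | True 10% vs 20%: recorded | Power | True 5% vs 10%: recorded | Power |
|---|---|---|---|---|
| 1 | 10% vs 20% | 51% | 5% vs 10% | 27% |
| 0.75 | 7.5% vs 15% | 39% | 3.75% vs 7.5% | 21% |
| 0.50 | 5% vs 10% | 27% | 2.5% vs 5% | 15% |
| 0.25 | 2.5% vs 5% | 15% | 1.25% vs 2.5% | 10% |

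Worked line for 10% vs 20%, f = 1: [0.10 × 10 − 1.96 × √(2 × 0.15 × 0.85)] / √(0.09 + 0.16) = (1 − 0.990) / 0.5 = 0.02, and Φ(0.02) = 0.51.

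Equal capture shrinks the absolute difference in proportion to f. Unequal capture could create a difference: a true rate of 20% in both groups, with capture of 70% in one and 50% in the other, is recorded as 14% and 10% (0.20 × 0.70 and 0.20 × 0.50), 4 points apart. Nothing in the documents shows that capture would differ between groups.

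**Window.** Leakage has a stated end (6 months); infection and ileus, in the same item, have none. Three-monthly contact exists but does not name complications, so capture after discharge is undefined.

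**The case against.** The strongest reply is that the serious abdominal infections after this operation are often leak-related. Leakage is a primary outcome with diagnostic criteria, no duration limit and 6 months of follow-up. Deaths are counted from the day of operation, and patients are seen every 3 months, with ultrasound and chest X-ray. Infection and ileus are not primary outcomes, and the 5-day rule reads the same for both groups. All of this stands. It narrows what is lost to short infections that are not leaks, plus the attribution of deaths; it does not justify the duration rule.

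Three stronger readings are tempting and should not be adopted.

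- A reader might infer that the list closes at discharge, because it sits beside drain removal and length of stay. That is possible, but no section says so. The list also holds leakage, which runs to 6 months, a urinary questionnaire covering the past month, and the pathology report. The accurate statement is that the window is unspecified.
- A reader might then infer that the group discharged earlier will look safer. That needs both closure at discharge and a difference in stay, and the documents establish neither.
- A reader might say that fatal infections vanish. They fail item 4 if they last 5 days or less, but the death itself is in overall survival.

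**Conclusion.** The concern holds in a limited form. The 5-day threshold is an explicit rule that counts infection by duration and ignores severity, so severe non-leak infections ending within 5 days are absent from a comparison meant to confirm safety. No window is stated for infection or ileus. Deaths are captured, but not by cause and not as perioperative mortality.

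The size of the undercount is unknown, and the power figures rest entirely on assumed rates and capture fractions. No bias for or against the new approach has been shown. The primary outcomes are unaffected. This is a cheap improvement, worth making because the reported infection rates and the safety statement built on them would change.

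**What to change.** In item 4, replace the duration threshold with every pulmonary or abdominal infection that needed treatment. Record its onset date, a standard severity grade (for example Clavien-Dindo) and its outcome including death. Report infections lasting more than 5 days as a subset, so the existing definition is not lost, and report perioperative deaths by group with cause.

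State one fixed window from surgery for infection and ileus in both groups, completed at the existing 3-monthly visits. Either the first visit or 6 months would serve; 6 months gives all of item 4 the same window as leakage.

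The cost is one changed case report form item and a few questions at visits already planned. Reported complication rates will be higher in both groups. The study started on 2020-12-01 and the protocol is dated 2021-09-07, so patients already operated on will need chart review, and that review should apply the same definition in both groups. Only data definition changes; patient care does not.

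### The safety objective has no recorded item for obturator nerve, obturator or iliac vessel, or ureter injury, the risks specific to the new dissection

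*Combined protocol and SAP*

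**What the plan says.** The Objective section states the aim: "To confirm the safety, feasibility and advantages by comparing the perioperative variables, postoperative functional and oncological outcomes of patients with ultralow rectal cancer", comparing the traditional transection with the gateway approach.

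Under Operating procedures in the Treatment section, the experimental steps open the peritoneum over the ureter and external iliac artery. Then: "The obturator vessels and obturator nerve are properly identified". The text adds a warning: "Care should be taken to avoid any injury when using energy devices near the obturator nerve". Where the surgeon finds it necessary, a loop is passed through the gateway and "the bundled S2-4 nerves, ureter and bladder vessels are gently retracted toward the cranial direction to widen the gap". The traditional steps in the same section describe none of this.

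Seven intraoperative variables follow: stapler angle, distance to the resection margin, conversion to a transanal approach, and "operative time, bleeding volume, anastomotic height from anal verge and the length of the stapling line". Postoperative management, item 4, lists the complications: "Whether complicated with anastomotic leakage, ileus and long-lasting (more than 5 days) pulmonary or abdominal infection". Item 2 covers the bladder: time of catheter removal, re-catheterization or medication, the IPSS questionnaire, and "residual urine volume in the bladder will be measured by ultrasound examination".

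Follow-up adds a general history and physical examination every 3 months for 3 years, IIEF-5 before surgery and at 1 year, and the Wexner score 3 and 12 months after stoma closure. Among the Primary outcomes, anastomotic leakage to 6 months is the only complication.

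**The concern.** A comparison meant to support a safety conclusion should count the harms that the new procedure could add. Here the added step is a dissection in the lateral pelvic compartment, and the protocol itself names a hazard there. Yet the complication list holds only leakage, ileus and prolonged infection, none of which is particular to that dissection.

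If the plan is followed as written, a final report could find leakage, ileus and infection similar in the two groups and call the approach safe, with no planned count of obturator nerve, vessel or ureter injury behind the statement.

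**Working it through.** **Step 1. Set the structures at risk against what is recorded.**

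| Structure in the experimental dissection | Dedicated item | Indirect information |
|---|---|---|
| Obturator nerve | None | General 3-monthly examination, no leg motor or sensory item |
| Obturator and external iliac vessels | None | Total bleeding volume, source not identified |
| Ureter | None | 24-hour fluid output; 3-monthly ultrasound; yearly MRI or CT; none read for injury |
| S2-4 nerves (retracted if necessary) | None | Catheter removal, residual urine, re-catheterization or medication, IPSS, IIEF-5, Wexner |

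No section describes open adverse-event collection or severity grading that would fill the first three rows. The fourth row is covered by function, with limits: IPSS has no stated baseline or time point, and the preoperative IIEF-5 is asked of men only.

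**Step 2. What recording would yield.** The Sample size section gives 100 experimental patients and at least 100 controls, with no event rate, alpha or power, so there is no planned figure to reproduce. The injury rates below are assumptions, shown as a range. Injury status is assumed known for all 100 patients.

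- Upper limit if no injury is seen (exact, two-sided 95%): 1 − 0.025^(1/100) = 0.0362, or 3.6%.
- Chance of at least one injury in 100, 1 − (1 − p)^100:
  - p = 1%: 1 − 0.99^100 = 0.634
  - p = 2%: 1 − 0.98^100 = 0.867
  - p = 5%: 1 − 0.95^100 = 0.994

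**Step 3. What recording would not yield.** Take 100 v 100, no events in controls, and an assumed two-sided alpha of 0.05. The Statistics section names Fisher's exact test but gives no alpha. Five v none gives p = 0.059; six v none gives p = 0.029. Significance therefore needs at least 6 injuries, and power is P(X ≥ 6) for X binomial(100, p):

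| Assumed true rate (controls 0%) | Power |
|---|---|
| 2% | 1.5% |
| 3% | 8.1% |
| 5% | 38.4% |
| 8% | 82.0% |

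A non-significant difference would thus say little about equality at rates below about 8%.

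**The case against.** The strongest reply is that the protocol does look at safety in several ways. Leakage is a primary outcome with a diagnostic definition and a 6-month window. Urinary, sexual and anal function would register consequences of pelvic nerve damage. Bleeding volume would reflect a serious vessel injury, and 3-monthly visits give a route by which a leg deficit or ureter problem could reach the chart. Retraction of the S2-4 nerves, ureter and bladder vessels is conditional, so not every experimental patient is exposed to it. Finally, 100 patients per group cannot compare rare injuries.

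Much of this stands. A reader might infer that pelvic nerve harm is not collected at all, that the harms of the new approach would never come to light, or that the trial can say nothing about safety. The documents do not support those readings, for the reasons just given.

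What does not stand is that these routes replace an injury item. None of the functional scores measures obturator nerve or ureter injury. Total bleeding does not show which vessel was hurt, or whether any was. An examination with no leg item, definition or planned rate produces notes rather than an outcome. The section on follow-up refers to the consent document for risks, and that document was not available for this review; describing a risk to patients would in any case not count its events. Low power between groups is a reason to limit the claim, not to leave the events unrecorded: an injury rate in the experimental group is informative by itself. That matters here because, for patients who accept either approach, the group depends on whether the stapler can reach more than 1 cm below the tumor, so the groups differ in difficulty.

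**Conclusion.** The gap is real and bounded. Injury to the obturator nerve, the obturator or iliac vessels, or the ureter has no recorded item, and there is no general adverse-event collection. S2-4 injury is visible only through functional measures, and vessel injury only through total blood loss. Safety against the risks specific to this dissection cannot be shown from the planned data, while the planned comparisons of leakage and function are unaffected.

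Without an injury item, no upper limit on these risks can be reported from planned data. With one, a clean record in 100 patients would exclude rates above 3.6%, and a true rate of 2% would probably show itself. Even then the result would be a bound on risk in the experimental group and not evidence of equal safety: power is about 38% at an assumed 5% v 0%. The rates and the alpha are assumptions; the absence of the items is read directly from the protocol.

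**What to change.** Add to the recorded variables, in both groups:

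- intraoperative injury to the obturator nerve, obturator or iliac vessels, ureter or bladder (yes/no, and type);
- new thigh weakness or numbness, at discharge and at the existing 3-monthly examination.

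Name these as safety outcomes and report the rates by group with exact 95% confidence intervals. State that they bound the risk in the experimental group and that a non-significant difference will not be read as equal safety.

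The study start is given as 2020-12-01 and the protocol is dated 2021/9/7, so check the charts of patients already operated on, and mark those data as retrospective. The cost is a few extra form fields and that chart check. No treatment or visit changes. Retrospective data may under-record mild deficits, which favors starting soon.
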